5.7. Other Analyses

5.7.1. Pharmacokinetics/Pharmacodynamic

PK analyses will be performed by the pharmacometrics group in clinical pharmacology on the PK analysis set (PKAS), defined as participants who have received at least 1 dose of JNJ-40411813 and have at least 1 valid blood sample drawn for PK analysis.

Descriptive statistics will be calculated for the plasma concentrations of JNJ-40411813 and concentrations of JNJ-40411813 metabolites including concentrations of JNJ-40411813 metabolites including applicable time point. If warranted and feasible, summary statistics will be provided for brivaracetam and additional column. Statistics include number of participants (N), number of observations (n), mean, standard deviation, coefficient of variation (CV), geometric mean, median, minimum, and maximum. PK data may also be displayed graphically, plotting boxplots of PK concentrations over time by treatment group.

Population PK analysis of JNJ-40411813 may be performed on the data of this study in combination with data pooled from other studies. An objective of these analyses is to investigate the potential effects of covariates, such as demographics and concomitant drugs, on the PK of JNJ-40411813. If conducted, the results of the population analyses will be reported separately from the clinical study report.

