# Safety assessments

Standard safety assessments including physical and neurological examination, vital signs, 12-lead ECG, clinical chemistry, hematology, and urinalysis will be performed.

Additionally, emergence of suicidal ideation will be assessed using the Columbia Suicide Severity Rating Scale (C-SSRS) (Posner 2007, See Section 11.9). The C-SSRS has been used frequently in clinical studies and is a standard measure for suicidal ideation assessment according to Food and Drug Administration (FDA) guidance (US FDA 2012).

CCI
CCI
Biomarkers
Blood samples will be collected to determine the plasma concentration of CCI

<sup>a This section has been amended by Amendment INT-1, INT-3, and INT-4

CCI
Pharmacokinetics
Blood samples will be collected to determine plasma concentration of JNJ-40411813 in plasma. The sampling days and times were selected so that population PK and/or PBPK analyses analysis could be conducted for the parent drug. The concentrations of metabolite CCI the most prominent metabolite in human plasma after repeated administration of JNJ-40411813, CCI which is equipotent to the parent drug for mGlu2, and CCI will be measured.
The plasma concentration of levetiracetam or brivaracetam will be measured so that safety, in the presence and absence of JNJ-40411813 may be assessed (i.e., confirm that circulating levels of levetiracetam or brivaracetam are not altered).
since
they were the most frequently used AEDs in the Phase 3 program of perampanel, an AED approved for the adjunctive treatment of partial-onset and primary tonic-clonic seizures in patients ≥12 years of age CCI (Majid 2016). In CCI
Pharmacogenomics
It is recognized that genetic variation can be an important contributory factor to interindividual differences in drug distribution and response and can also serve as a marker for disease susceptibility and prognosis.

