# 6.5. Concomitant Therapyb

All prestudy therapies administered up to 30 days before screening must be recorded at screening (and confirmed by treating physician).

During the 8-week prospective pretreatment baseline period and during the 12-week double-blind treatment period, participants will continue to take their prescribed AEDs (one of which must include levetiracetam or brivaracetam) without change in dosage(s); new concomitant AEDs should not be added. For the concomitant AEDs including levetiracetam or brivaracetam, all doses within the limits of current clinical practice will be allowed. Concomitant AEDs will not be provided by the study sponsor.

Two exceptions to this rule will be allowed:

<sup>a This section has been amended by Amendment INT-1

[figure not shown]
b This section has been amended by Amendment INT-1

- Based upon clinical judgment, a one-time dosage adjustment of concomitant AEDs is permitted to mitigate adverse events attributable to those AEDs. Collection of blood for plasma concentration of these AEDs is allowed, at the discretion of the investigator.
- One-time changes in AED dosages do not represent a change in the daily AED regimen. For example, if the participant took an extra dose of an AED on one day, this would not represent a change in the daily AED regimen.

Rescue medication may be used as needed (PRN). Each administration of rescue medication must be documented in the seizure e-diary. However, benzodiazepines or barbiturates received on a continuing basis at stable dosages for 1 month before screening should be considered as concomitant AEDs. Benzodiazepines or barbiturates used as sleep aid or to treat anxiety will be allowed but should be documented in the eCRF.

For levetiracetam or brivaracetam drug intake on the days of study visits, the same rule applies as for JNJ-40411813: On the day of Visits 2, 4, 6 and 7 CCI will be taken in the study center during the study visit and CCI. Dosing during the site visit will be witnessed by the study staff. CCI. Participants taking levetiracetam XR should preferably take their medication in the morning and take this medication in the clinic during Visits 2, 4, 6 and 7. If the participant takes levetiracetam XR in the evening, this should not be changed for the study.

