# 9.3. PK and PK/PD analysesa

Data for all participants who receive a dose of JNJ-40411813 and have at least one measurement of plasma concentration, will be included in the PK analysis. Plasma concentrations of JNJ-40411813 and metabolites including CCI levetiracetam/ brivaracetam and will be listed for all participants who received this active medication.

Descriptive statistics will be calculated for the plasma concentrations of JNJ-40411813 and metabolites including CCI levetiracetam/ brivaracetam and CCI at each applicable

time point. Statistics include sample size (n), mean, standard deviation, coefficient of variation (CV), geometric mean, median, minimum, and maximum.

Population PK and/or PBPK analyses of JNJ-40411813 and levetiracetam/brivaracetam may be performed on the data of this study in combination with data pooled from other studies. An objective of these analyses is to investigate the potential effects of covariates, such as demographics and concomitant drugs, on the PK of JNJ-40411813. The results of the population analyses may be reported separately.

PK and PD relationship will be explored, if feasible. The results of population PK/PD analyses will also be reported separately.

\_

<sup>a This section has been amended by Amendment INT-1

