4. POPULATIONS (ANALYSIS SETS) FOR ANALYSIS

For purposes of analysis, participants will be classified into the following analysis sets. For each analysis set described below, participants will be analyzed according to the planned study intervention irrespective of what they actually received.

Analysis Sets	Description				
Enrolled	All participants who sign the ICF.				
Randomized The randomized analysis set includes all participants who were randomized in					
Full Analysis Set	The full analysis set (FAS) includes all randomized participants assigned to receive				
(FAS)	study intervention and have both baseline and postbaseline seizure data. This definition				
	is the same as the ITT set.				
Full Analysis Set:	The FASOLE analysis set includes all FAS participants who received at least 1 dose of				
Open-Label	study intervention in the OLE phase.				
Extension					
(FASOLE)					
Compliance	The compliance analysis set (CAS) includes a subset of participants in the FAS who				
Analysis Set	were in compliance with their medication intake. In other words, exclude those who with				
(CAS)	<80% compliance for medication intake. Medication intake data will come from the dru				
	accountability data collected at monthly visits.				
"Modified" FAS	The modified FAS includes a subset of participants in the FAS who remained in the				
	treatment period beyond 4 weeks. In other words, participants who exit the study by 4				
	weeks having reached their pre-randomization baseline seizure count will not be				
	included.				
Safety (SAF)	The safety analysis set includes all randomized participants who received at least 1 dose				
C-f-t O	of JNJ-40411813 or placebo in the double-blind phase.				
Safety: Open-	The SAFOLE analysis set includes all randomized participants who received at least 1				
Label Extension dose of study intervention in the OLE phase. This analysis set is the same as the					
(SAFOLE)	FASOLE analysis set.				
PK Analysis Set	The PK analysis set (PKAS) included all randomized participants who have received at				
(PKAS)	least 1 dose of JNJ-40411813 and have at least 1 valid blood sample drawn for PK				
	analysis.				

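### The PK analysis set leaves out the placebo arm, so the levetiracetam and brivaracetam summaries have no randomised control for the question of whether background levels change

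*SAP*

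**What the plan says.** **Purpose.** The pharmacokinetics paragraph of protocol 4.2 explains why the background drug is assayed: so that safety "in the presence and absence of JNJ-40411813 may be assessed", spelled out as to "confirm that circulating levels of levetiracetam or brivaracetam are not altered". The PK of levetiracetam or brivaracetam is also a secondary objective (protocol 3, SAP 1.1), with concentrations on Day 1 and at Weeks 4, 8 and 12 as the endpoint.

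**Collection.** The Schedule of Activities and protocol 8.5, Table 4, place these samples at Visits 2, 4, 6 and 7 without restricting them to one arm.

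**Analysis.** SAP 5.7.1 bases all PK analyses on one population, the PK analysis set (PKAS). This is "defined as participants who have received at least 1 dose of JNJ-40411813"; a usable PK sample is required as well. SAP 4 defines the set the same way. Protocol 9.3 is the source of the restriction: "Data for all participants who receive a dose of JNJ-40411813 and have at least one measurement of plasma concentration". No other set is defined for background-drug concentrations. SAP 5.7.1 also offers optional boxplots over time by treatment group.

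**AED dose changes.** AEDs should stay constant, but protocol 6.5 says "a one-time dosage adjustment of concomitant AEDs is permitted to mitigate adverse events attributable to those AEDs", and inclusion criterion 5 allows reductions for suspected high AED levels or side effects.

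**The concern.** The question of altered background levels needs a comparison of exposure with and without JNJ-40411813. Randomisation supplies one, and the placebo samples are scheduled, but the analysis set then excludes them. What remains is change over time in treated participants. That cannot separate an interaction from drift in adherence, from differences in time since the last dose, or from AED dose changes made during treatment.

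The last of these may differ between arms. Protocol 4.2 attributes dizziness and fatigue to JNJ-40411813 and notes reports of somnolence. Protocol 2.2.3 and 2.2.4 list overlapping effects for the two background drugs. An investigator who attributes such an event to the background AED may reduce it, so reductions could be more common on active treatment. The planned statistics are of concentrations, with no normalisation to AED dose stated.

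**Working it through.** The plan gives no figure to reproduce. The check compares its passages and makes two small calculations.

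**1. Who is in the set**

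| Step | Placebo participants included? |
|---|---|
| Purpose (protocol 4.2) | The no-JNJ condition is part of the question |
| Sampling (Schedule of Activities, Table 4) | Yes |
| PK summaries (SAP 4, SAP 5.7.1, protocol 9.3) | No, unless JNJ-40411813 is taken later |

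Neither SAP definition names a study phase. A placebo participant who takes JNJ-40411813 in the open-label extension would meet the dose condition on a literal reading. Those participants are self-selected and are not the randomised placebo arm. Boxplots drawn from this set cannot show JNJ-40411813 against placebo.

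**2. How many samples are left out**

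- Table 4, levetiracetam or brivaracetam: Visit 2 (2) + Visit 4 (2) + Visit 6 (1) + Visit 7 (1) = 6 per participant.
- Placebo participants (protocol 6.3): about 20 in Cohort 1 and 10 in Cohort 2, so 30.
- Ceiling: 30 × 6 = 180.
- Once-daily evening XR users give one sample per visit (Table 4 footnote): 1 + 1 + 1 + 1 = 4. If all 30 were such users, the count would be 30 × 4 = 120.
- A participant on the standard schedule who exits at Week 4 gives 2 + 2 = 4, because the early-withdrawal PK sample is taken only after Visit 6 (Schedule of Activities, footnote m).
- If Cohort 3 runs with 10 more placebo participants, the group is 40 of 160 randomised (25%).

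**3. What the before-after comparison can use**

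- Predose samples at Visits 2, 4 and 6 compare directly.
- Post-dose samples do not: 2 hours at Visit 2, 1 hour at Visit 4, and no fixed interval at Visit 7. Placebo participants follow the same schedule, so a same-visit comparison between arms avoids the mismatch.
- For evening XR users the Visit 2 sample is drawn with the post-dose JNJ-40411813 sample, 2 hours after the first dose. They have no sample from before study drug.

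**4. How far AED dose reductions could distort raw means**

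Assumptions, for illustration only: JNJ-40411813 raises exposure by 50% (×1.5); a fraction f of active participants goes from 3,000 to 2,000 mg/day of levetiracetam (×2/3); starting levels are equal. A participant with the reduction has ratio 2/3 × 1.5 = 1.0. The mean ratio is (1 − f) × 1.5 + f × 1.0.

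| f | Mean ratio |
|---|---|
| 10% | 1.35 + 0.10 = 1.45 |
| 20% | 1.20 + 0.20 = 1.40 |
| 100% | 1.00 |

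The reductions dilute the signal. They remove it only if nearly every active participant has one.

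**The case against.** The strongest reply is that the question keeps a reference. Protocol 4.2 does not promise a comparison with placebo; Visit 2 predose is a no-JNJ condition and the later visits are the exposed one. Comparing participants with themselves removes differences in dose and clearance between people. AEDs are meant to stay constant, and intake and sampling times are recorded (protocol 6.4, 6.6 and 8.5). Protocol 8.5 lists concentrations for all participants who have them. Protocol 9.3 allows population PK of levetiracetam and brivaracetam. The analysis is descriptive, secondary and Phase 2a.

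Much of this stands. A reader might infer that the question cannot be answered at all; that is too strong, because most active participants have a usable predose reference. A reader might also infer that AED dose reductions would conceal an interaction; the calculation shows that this needs near-universal reductions, which nothing in the documents suggests. Nor do the documents report any effect of JNJ-40411813 on levetiracetam or brivaracetam levels, so they do not support reading a seizure benefit as an exposure artefact.

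The rest does not close the gap. A listing is not an analysis, and protocol 9.3 confines its own listing to recipients of active medication. The population PK analysis is optional, and SAP 5.7.1 names only JNJ-40411813 for it. The analyte sentence in SAP 5.7.1 is partly unreadable, so what is summarised for levetiracetam cannot be judged, but the set definition is legible.

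**Conclusion.** The point holds as an avoidable weakness in a secondary descriptive analysis. Followed as written, the randomised control for background-drug levels is zero, apart from placebo participants who later take JNJ-40411813 in the extension. About 30 placebo participants over Cohorts 1 and 2, with at most about 180 samples, are left out. These are planned numbers and assume that every placebo participant is sampled as scheduled. The before-after comparison that remains is usable for most active participants but uncontrolled, and it is unavailable for evening XR users. The primary Cox analysis is not touched. The change is worth making because the samples and intake times are already being collected.

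**What to change.** In SAP 4 and 5.7.1, define a background-AED concentration set: all randomised participants who took one or more doses of double-blind study drug, active or placebo, and have one or more valid levetiracetam or brivaracetam samples. Align protocol 9.3, or declare the departure in SAP 6.2, which now states that there are none. Keep the PKAS for JNJ-40411813 and its metabolites.

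On the new set:

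- Summarise concentrations, normalised to the AED dose being taken, by arm, visit and sampling time.
- Where a Visit 2 predose sample exists, summarise by arm the within-participant ratio of the Visit 4 and Visit 6 predose values to it. For levetiracetam, add a descriptive JNJ-to-placebo geometric mean ratio with 95% CI.
- For brivaracetam, give descriptive statistics only if numbers are too small. It enters from Cohort 2, where about 10 placebo participants are shared between the two drugs.
- Compare evening XR users between arms at the same visit, since their ratio to a Visit 2 predose value cannot be formed.

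The cost is wording, assay of placebo samples already drawn, and one more table, with no change at sites. The intervals will be wide because the placebo arm is small, so the result should be read as descriptive.

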5.7.2. Pharmacokinetics/Pharmacodynamic Relationships

If deemed feasible, exploratory PK-PD analyses, including graphical exploration of PK-PD data, may be explored. If conducted, results of such analyses will be reported separately.

5.7.3. Biomarkers

During the study, blood will be collected at Visit 2 (baseline), Visit 4 and Visit 7/EW for the potential assessment of the biomarkers Biomarkers may be added or deleted based on scientific information or technical innovations. Details of the exploratory biomarker analysis, if conducted, will be provided in a separate document.

5.8. Interim Analyses

This study has an Interim Review Committee (IRC) who will conduct interim reviews unblinded at the individual level. In Cohorts 1 and 2, after all participants in a cohort have completed 4 weeks of treatment, the IRC will review all cumulative safety, PK and efficacy data of JNJ-40411813 available to that date to provide recommendation on study progression. If the results after the last participant has completed the 4-week visit are inconclusive with respect to the assessment of

efficacy, a second interim review of the same cohort may be done after the last participant has completed the 12-week visit.

5.8.1. Data Monitoring Committee (DMC) or Other Review Board

Continuous or periodic blinded safety reviews will be done by the SRP. If there are safety concerns from these reviews, a Data Review Committee (DRC) will be called upon to conduct an unblinded review of the data at the individual participant level. The DRC will consist of at least one medical expert from the relevant therapeutic area and at least one statistician.

A separate short SAP detailing the deliverables and the decision criteria will be written for the DRC and IRC respectively, and will be completed before the first interim review.

SUPPORTING DOCUMENTATION 6.

6.1. **Appendix 1 List of Abbreviations**

ADA anti-drug antibody adverse event ΑE **AED** Anti-epileptic drug ALT/SGPT alanine aminotransferase analysis of covariance **ANCOVA** AST/SGOT aspartate aminotransferase anatomic and therapeutic class ATC

area under the curve **AUC** body mass index **BMI** body surface area **BSA** CAS Compliance analysis set CI confidence interval total systemic clearance CLCmax maximum concentration

CRF case report form Clinical Study Report **CSR**

C-SSRS Columbia Suicide Severity Rating Scale

Common Terminology Criteria for Adverse Events **CTCAE**

coefficient of variation CV DB Double-Blinded

DMC Data Monitoring Committee Data Presentation Specifications DPS DRC Data Review Committee

electrocardiogram **ECG**

electronic Case Report Form eCRF

Early Withdrawal EW

F (%) absolute SC bioavailability

FAS full analysis set

Food and Drug Administration **FDA**

ICH International Conference on Harmonisation

interquartile IQ

IRC Interim Review Committee **IVRS** interactive voice response system **IWRS** interactive web response system lower limit of quantification LLOQ **LOCF** last observation carried forward

Medical Dictionary for Regulatory Activities MedDRA

minimum required dilution **MRD** neutralizing antibodies NAb Open Label Extension **OLE** pharmacodynamic(s) PD PΙ principal investigator PK pharmacokinetic(s) PP per protocol

SAE serious adverse event Statistical Analysis Plan SAP SD Standard Deviation

SMQs standardised MedDRA queries **SRP** Senior research physician

TEAE treatment-emergent adverse event time to maximum concentration Tmax United States National Cancer Institute US NCI

V volume distribution Vz volume of distribution based on terminal phase

Vz/F apparent volume of distribution based on terminal phase after extravascular administration

WHO World Health Organization

WHO-DD World Health Organization Drug Dictionary

ADA anti-drug antibody AE adverse event

ALT/SGPT alanine aminotransferase
ANCOVA analysis of covariance
AST/SGOT aspartate aminotransferase
ATC anatomic and therapeutic class

AUC area under the curve
BMI body mass index
BSA body surface area
CI confidence interval
CL total systemic clearance
Cmax maximum concentration
CRF case report form

CSR Clinical Study Report

CTCAE Common Terminology Criteria for Adverse Events

CV coefficient of variation
DMC Data Monitoring Committee
DPS Data Presentation Specifications

ECG electrocardiogram

eCRF electronic case report form F (%) absolute SC bioavailability

FAS full analysis set

FDA Food and Drug Administration

ICH International Conference on Harmonisation

IQ interquartile

IVRS interactive voice response system
IWRS interactive web response system
LLOQ lower limit of quantification
LOCF last observation carried forward

MedDRA Medical Dictionary for Regulatory Activities

MRD minimum required dilution
NAb neutralizing antibodies
PD pharmacodynamic(s)
PI principal investigator
PK pharmacokinetic(s)
PP per protocol

SAE serious adverse event SAP Statistical Analysis Plan SD standard deviation

SMQs standardised MedDRA queries
TEAE treatment-emergent adverse event
Tmax time to maximum concentration

US NCI United States National Cancer Institute

V volume distribution

Vz volume of distribution based on terminal phase

Vz/F apparent volume of distribution based on terminal phase after extravascular administration

WHO World Health Organization

WHO-DD World Health Organization Drug Dictionary

6.2. Appendix 2 Changes to Protocol-Planned Analyses

There have been no changes to protocol-planned analyses.

6.3. Appendix 3 Demographics and Baseline Characteristics

The number of participants in each analysis set will be summarized and listed by treatment group, and overall. In addition, the distribution of participants by country and site ID will be presented unless otherwise noted.

Table 4 and Table 5 present a list of the demographic variables and baseline characteristics respectively, that will be summarized by treatment group and overall for the safety analysis sets (SAF and SAFOLE). Demographics will also be summarized by within treatment group using the safety analysis set.

Table 4: Demographic Variables

Continuous Variables:	Summary Type	
Age (years)	Descriptive statistics (N, mean, standard deviation [SD], median	
Weight (kg)		
Height (cm)	and range [minimum and	
Body Mass Index (BMI) (kg/m²)	maximum])	
Categorical Variables		
Age (18-25 years, 26-50 years, 51-64 years, and $\geq = 65$ years)		
Sex (male, female, undifferentiated)	Frequency distribution with the number and percentage of participants in each category.	
Region ^a (America, Asia, Eastern Europe, Western Europe)		
Race ^b (American Indian or Alaska Native, Asian, Black or African		
American, Native Hawaiian or other Pacific Islander, White, Multiple)		
Ethnicity (Hispanic or Latino, not Hispanic or Latino)		
BMI (underweight <18.5 kg/m ² , normal 18.5-<25 kg/m ² , overweight 25-		
$<30 \text{ kg/m}^2$, obese $>=30 \text{ kg/m}^2$)		

^a America includes Canada, USA; Asia includes Australia, Japan, South Korea; Eastern Europe includes Russia, Turkey, Ukraine; Western Europe includes Belgium, France, Germany, Greece, Italy, Netherlands, Portugal, Spain, UK

Table 5: Baseline Characteristics

Continuous Variables:	Summary Type
CCI	Descriptive statistics (N, mean,
Baseline monthly seizure count	standard deviation [SD], median
	and range [minimum and
	maximum], and IQ range).
CCI	
Seizure type (focal aware seizures with and without motor signs, focal	Frequency distribution with the number and percentage of participants in each category.
impaired awareness seizures, focal to bilateral tonic-clonic seizures, other)	
Cluster seizures (proportion of participants who report cluster seizures)	
AED use (Levetiracetam etc)	
Number of baseline AED's used (1,2,3,4)	

b If multiple race categories are indicated, the Race is recorded as 'Multiple'

